3.2 End of Treatment

The total duration of Palbociclib treatment is 12 days, beginning any time after enrollment. Definitive surgery will occur 3 (+/- 1day) after end of palbociclib treatment, on study day #15 +/- 1 day. The end of treatment visit will occur 32 (+/- 8 days) after surgery. Unless a patient discontinues treatment early or experiences treatment delays, this would result in 24-40 days on trial. Any premature, permanent termination of IP treatment is referred to as "Early End of IP-treatment". "End of IP treatment per protocol" means Palbociclib treatment ended after 12 days.

Any one of the following criteria will be reason to stop IP-treatment before 12 days:

- General or specific changes in the participant's condition render the participant not a candidate for further treatment in the opinion of the treating investigator
- Unacceptable toxicity or unacceptable adherence to palbociclib.
- Patient withdraws consent

3.3 End of Study

The study ends when all enrolled patients complete trial procedures.

End of study is the date when the last patient has completed their end of study visit, all data have been collected, and all queries have been resolved.

The study may be terminated in case of excessive toxicity (please refer to section “**4.6.2 Study Termination**”) or if deemed not feasible (section “**2.3 Outcome Measures; feasibility**”).

3.3.1 End of Study Visit

Patient’s end of study visit is the last formal study visit, or last formal contact or an unscheduled study visit in case of early withdrawal from all Phases of the study for treatment and follow-up.

3.3.2 Managing Patients Who Never Received Protocol Treatment

Patients who never received definitive surgery will be substituted.

Patients who are enrolled to the trial on Group A, but never received Palbociclib will be substituted.

3.3.3 Patients Lost to Follow Up

During the duration of the study, sites will be expected to continue efforts to contact all enrolled patients as well as regularly consult publicly available information to ascertain vital status of the patient. After End of study visit, patients will allow long term follow up through medical records review for medical history, additional treatments, disease and survival status, as well as a telephone call at 1yr and at 5yrs from definitive surgery. In cases where sites cannot successfully contact a patient and is not able to receive appropriate publicly available information for greater than two years, the patient will be noted as lost to follow up.

3.4 Rationale for Study Design

3.4.1 Rationale for Test Product Dosage (Palbociclib)

Choice of palbociclib dose: A smaller than approved dose was selected for safety concerns, minimizing the risk of neutropenia in the pre-operative period. We expect this dose to be efficacious against the early stage lesions from enrolled patients based on described experience in palbociclib study A5481001⁴². In that single agent escalation study plasma pharmacokinetics parameters had low variability with a small dose-dependent increase in exposure over the dose range of 100 to 150 mg, based on Cmax and AUC from 0 to 10 hours. The dose limiting toxicity was neutropenia. During cycle #1 the more severe neutropenia reported at 100mg daily was graded as 2 (CTCAE). With 125mg daily, neutropenia reached grade 3.

A) Group A (Palbociclib treatment)

Group A will receive palbociclib 100mg by mouth daily for 12 days prior to definitive surgery.

Palbociclib will be provided by Pfizer.

B) Group B (Observation)

Group B will receive no preoperative treatment.

3.4.2 Rationale for Choice of Regimen

Choice of palbociclib treatment duration: Typical interval between diagnostic biopsy and definitive surgery in DCIS varies from 7-28 days. This is the interval in which enrollment, screening and treatment will take place in this study. In the phase I A palbociclib escalation study A5481001⁴², patients were treated for 2 on/1 off weeks or for 3 on/1 off weeks. In the 3 on/1 off group, neutropenia and thrombocytopenia nadir occurred between days 15 and 22 of uninterrupted treatment. In another phase I trial of palbociclib in combination with chemotherapy, metastatic tumor biopsies performed after 7 days of palbociclib single agent demonstrated histologic changes in comparison to pretreatment biopsy in some patients ([NCT01522989](#))⁵⁴. In a neoadjuvant trial of palbociclib and anastrozole presented at SABCS 2015, 8 patients with invasive breast cancer received a delayed course of palbociclib 125 mg QD for 10 to 12 days until the day prior to surgery, to address Ki67 changes in tissue⁵⁵. There were no delays on surgery date due to toxicity. Therefore, we decided to treat patients for 12 days to ensure safe and adequate exposure to drug.

4. MATERIALS AND METHODS

4.1 Patients

4.1.1 Inclusion Criteria

Inclusion criteria for all patients (Groups A and B):

Inclusion Criteria for all patients (Groups A and B)	
I.1	Signed informed consent obtained prior to any study specific assessments and procedures
I.2	Age ≥ 18 years
I.3	Premenopausal and postmenopausal women, or men
I.4	Current pathologic diagnosis of DCIS of the breast of any receptor status; History of previous DCIS allowed provided that the patient is currently off systemic risk-reduction endocrine therapy; History of previous invasive breast cancer adequately treated and that is currently in remission and unrelated to current DCIS (based on primary tumor location) is allowed as long as patient is currently off systemic therapy for that invasive cancer for at least 4 weeks prior to pre-treatment biopsy (diagnostic biopsy); Patients with multifocal or multicentric lesions are allowed, as long as at least one lesion

	is histologically confirmed DCIS and overall clinical AJCC Stage 0 or I.
I.5	A formalin-fixed paraffin-embedded (FFPE) tumor tissue block from diagnostic biopsy must be transmitted to MedStar Georgetown University Hospital Pathology Department repository and confirmation of receipt must be available prior to enrollment.
I.6	Positive Rb by immunohistochemistry in the DCIS component of the lesion Must be performed at CLIA-approved setting (for instance, MGUH) Rb staining will be considered positive when 1+ or above (in a scale of 0, 1+, 2+ or 3+)
I.7	In the absence of histologic diagnosis of DCIS, patient may undergo fresh biopsy for eligibility, provided: This invasive procedure is not a Fine Needle Aspiration (FNA); AND This procedure is a core biopsy, stereotactic biopsy or incisional biopsy of the suspicious breast lesion; AND The primary lesion is not completely resected during the procedure.
I.8	The patient is candidate for and is willing to receive definitive surgical therapy for DCIS
I.9	ECOG performance status 0-1 (Appendix G: ECOG PS scale).
I.10	Willingness to provide a sample of tissue collected at definitive surgery for research.

Inclusion criteria specific to treatment Group A:

Inclusion Criteria specific for patients enrolled on Group A	
I.11	Patients must be able and willing to swallow and retain oral medication
I.12	Absolute neutrophil count (ANC) $\geq 1,500/\text{mm}^3$
I.13	Platelets $\geq 120,000/\text{mm}^3$
I.14	Hemoglobin $\geq 10\text{g/dL}$
I.15	Total serum bilirubin $\leq \text{ULN}$; or total bilirubin $\leq 3.0 \times \text{ULN}$ with direct bilirubin within normal range in patients with documented Gilbert's Syndrome.
I.16	Aspartate amino transferase (AST or SGOT) and alanine amino transferase (ALT or SGPT)

	$\leq 1.5 \times$ institutional ULN
I.17	Serum creatinine within normal institutional limits or creatinine clearance ≥ 50 mL/min/1.73 m ² for patients with serum creatinine levels above institutional ULN.
I.18	
Pregnancy must be ruled out:
 
Serum or urine pregnancy test must be negative within 14 days of treatment start in women of childbearing potential.
 
Pregnancy testing does not need to be pursued in patients who are judged as postmenopausal before enrollment, or who have undergone tubal ligation, bilateral oophorectomy, total hysterectomy

I.19	
Willingness to undergo adequate contraception if childbearing potential
 
Women of childbearing potential and male patients randomized into treatment Group A must use adequate contraception for the duration of protocol treatment and for 3 months after the last treatment with palbociclib if they are in Group A.
 
Adequate contraception is defined as one highly effective form (i.e. abstinence, (fe)male sterilization) OR two effective forms (e.g. non-hormonal IUD and condom / occlusive cap with spermicidal foam / gel / film / cream / suppository).

There will be no specific criteria for Group B since this is a biorepository only group.

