4.1.2 Exclusion Criteria

Exclusion criteria for all patients (Groups A and B):

Exclusion Criteria for all patients (Groups A and B)	
E.1	Concurrent therapy with other Investigational Products.
E.2	
Invasive carcinoma present in the diagnostic biopsy
 
Microinvasion is allowed

E.3	Uncontrolled intercurrent illness including (active infection, symptomatic congestive heart failure, unstable angina pectoris, cardiac arrhythmia, diabetes, pulmonary embolism in the past 6 months, or psychiatric illness/social situations that would limit

	compliance with study requirements).
E.4	Unable to comply with study requirements
E.5	Hormone therapies containing estrogen, progesterone, GnRH agonists and antagonists within 4 weeks from diagnostic biopsy.
E.6	Therapy with any CDK inhibitor in the past 3 months

Exclusion criteria specific to treatment Group A:

Exclusion Criteria Specific for patients enrolled on Group A	
E.7	History of allergic reactions attributed to compounds of chemical or biologic composition similar to palbociclib
E.8	Presence of a condition that would interfere with enteric absorption of palbociclib
E.9	Pregnant women, or women of childbearing potential without a negative pregnancy test (serum or urine) within 7 days prior to enrollment Breastfeeding must be discontinued prior to study entry (Group A only).
E.10	Patients on combination antiretroviral therapy, i.e. those who are HIV+ (potential for pharmacokinetic interactions or increased immunosuppression with palbociclib).
E.11	Patients receiving any medications or substances that are potent inhibitors or inducers of CYP3A isoenzymes within 7 days of enrollment or during participation on study (see Section 4.4.5 Prohibited Therapy for list of CYP3A inhibitors and inducers).
E.12	Patients with clinically significant history of liver disease, including viral or other known hepatitis, current alcohol abuse, or cirrhosis, etc.

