- 1) Signed and dated Eligibility Checklist (Appendix E); filled out completely and signed by investigator.
- 2) Signed and dated Lombardi Patient Registration Form (Appendix F). Typically, this form is signed by study coordinator. Exceptionally, in the absence of the study coordinator, this form can be signed by the investigator.
- 3) Signed and dated informed consent form
- 4) Signed and dated HIPAA form
- 5) All source documents required for verification of eligibility:
 - a) Pathology report stating diagnosis of DCIS
 - b) Confirmation of retrieval of archival tissue from diagnosis of DCIS

- c) Pathology report stating Rb status positive
- d) Tentative date for definitive surgery (Lumpectomy, Mastectomy, etc)
- e) Clinic notes containing information on ECOG PS, previous and current treatments, co-morbidities, and information pertaining to eligibility for the trial
- f) Current negative beta HCG test report (blood or urine) for women of childbearing potential
 - *Group A only*
- g) Current Complete Blood Count with differential and Platelets – *Group A only*
- h) Current Bilirubin levels and normal range at local laboratory – *Group A only*
- i) Current Creatinine levels and normal range at local laboratory – *Group A only*
- j) Current AST levels and normal range at local laboratory – *Group A only*
- k) Current ALT levels and normal range at local laboratory – *Group A only*

The **informed consent form** should be uploaded to the patient's electronic medical record system, in addition to keeping the physical document signed by the patient and treating physician in the study binders, as per standard operating practice.

All participants must be registered and enrolled through the Oncology Research office at MedStar Georgetown University Hospital.

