4.4 Concomitant Therapy

All prior treatment or medication administered during the 30 days prior to enrollment and any concomitant therapy administered to the patient throughout the study until date of surgery must be recorded on the respective page of the eCRF. The generic or trade name of the drug must be specified along with the dose, the duration of treatment, relation to AE and indication for use.

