4.4.3 Hormone Therapy

Hormone therapy is not allowed during the trial. Patients receiving hormone therapy for previous diagnosis of DCIS or invasive cancer should discontinue this therapy at least 4 weeks prior to undergoing pre-treatment biopsy.

Hormone replacement therapies are allowed except for estrogen, progesterone, GnRH agonists and antagonists. Examples of allowed hormone therapies are insulin and levothyroxine.

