4.5.2 Screening phase

The Screening Phase is the time between the date a patient provides written informed consent, and the time the patient completes enrollment procedures/has enrollment verified by the Lombardi Project Manager (PM). Data collection and procedures during this time period include patient demographics, eligibility requirements, concomitant medications, medical history, physical examination/vital signs, ECOG performance status assessment, baseline symptoms/adverse events, severe adverse events, laboratory measurements, pregnancy testing (if applicable), biospecimens (blood and tissue sample #1), and Rb testing. During the Screening Phase, only AEs deemed to be serious (SAEs) and related to protocol mandated and not routinely performed procedures have to be reported.

4.5.2.1 *Pathologic diagnosis of DCIS - Biopsy*

This procedure must be completed before registration by LCCC PM to trial. Typically, patient will be offered the trial after pathologic diagnosis of DCIS. However, the trial may be offered to patients prior to diagnostic biopsy, in case of highly suggestive radiological findings for DCIS. In this case, patients will need to complete diagnostic biopsy for eligibility. Fine needle aspiration is not acceptable. Patient can

undergo core biopsy, stereotactic biopsy or incisional biopsy of breast lesion, as long as the lesion is not completely resected during the procedure.

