Appendix F: Lombardi Patient Registration Form

INSTRUCTIONS FOR STUDY COORDINATOR: This 2-page form and all supporting documentation should be completed by the research staff and scanned/mailed to [REDACTED]
[REDACTED] and [name], [REDACTED]
[REDACTED]

Patient Initials: _____ Study ID (IRB#): **2018-0075**

Study Coordinator name: _____ Signature: _____

Date _____/_____/_____

1. Site PI: _____

2. Enrolling MD: _____

3. Date Informed Consent signed: _____/_____/_____

4. Date HIPAA authorization signed: _____/_____/_____

5. Study Group: () Group A (pre-operative 12-day course of Palbociclib 100mg daily PO)
() Group B (No pre-operative treatment)

6. Proposed start date for Palbociclib (Day 1) () Group A: _____/_____/_____
() Group B: *Non applicable*

7. Date of Pathological diagnosis of DCIS: _____/_____/_____

8. Please email **eligibility packet** to: (1) LCCC PM; and to (2) Sponsor-PI [name]

 Lombardi Patient Registration Form (Appendix F) - this form filled out completely and signed by the Study Coordinator	 Tentative date for definitive surgery (Lumpectomy, Mastectomy, etc.)
 Eligibility Checklist (Appendix E) filled out completely and signed by the Investigator	 Physician's Note
 Signed and dated informed consent form	 ECOG score
 Signed and dated HIPAA form	 Past Medical History
 Pathology Report stating DCIS diagnosis	 Concomitant medication list
 Pathology Report stating DCIS is Rb +	 Current negative beta HCG test report (blood or urine) for women of childbearing potential – Group A only
 Confirmation of retrieval of archival tissue from diagnosis of DCIS	 Laboratory Results (CBC, CMP) – Group A only
	 Other _____

ON-STUDY CARD – Study 2018-0075

MRN: _____

DOB: ____/____/_____

Treating Physician _____ RN _____

Zip Code: _____

Race African American
 Asian
 Caucasian
 Hispanic
 Native American
 Pacific Islander
 Other
 Unknown

Gender: Male Female Unknown

Ethnicity: Hispanic or Latino
 Not Hispanic or Latino
 Unknown

Consent Approval Date: ____/____/_____

Screen Failure Yes No

On Study Date ____/____/_____

Protocol Waiver: Yes No

Reason _____

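### Inclusion criterion I.4 sets no pre-biopsy endocrine washout for prior DCIS, although section 4.4.3 asks for four weeks, so the baseline core may be taken on therapy

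*Combined protocol and SAP*

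**What the plan says.** Four provisions bear on hormone therapy before the baseline biopsy.

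- **I.4, prior DCIS** (synopsis, section 4.1.1, Appendix E): "History of previous DCIS allowed provided that the patient is currently off systemic risk-reduction endocrine therapy". No duration is given and nothing ties the condition to the biopsy.
- **I.4, prior invasive cancer** (same three places): the patient must be "off systemic therapy for that invasive cancer for at least 4 weeks prior to pre-treatment biopsy (diagnostic biopsy").
- **Section 4.4.3, Hormone Therapy:** patients on hormone therapy for a "previous diagnosis of DCIS or invasive cancer should discontinue this therapy at least 4 weeks prior to undergoing pre-treatment biopsy". This covers both histories.
- **E.5, section 4.1.2:** excludes "Hormone therapies containing estrogen, progesterone, GnRH agonists and antagonists within 4 weeks from diagnostic biopsy". It names no tamoxifen, raloxifene or aromatase inhibitor, which are the agents that section 1.1 describes as endocrine risk reduction.

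On timing, section 4.5.2.1 states: "Typically, patient will be offered the trial after pathologic diagnosis of DCIS". Sections 2.2.1 and 2.3 make the diagnostic core (Sample #1) the baseline for the primary within-patient comparison with tissue from definitive surgery (Sample #2).

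**The concern.** A washout that must be complete before the biopsy cannot be arranged once the biopsy has been taken. For most candidates section 4.4.3 can therefore work only as an eligibility condition, and the eligibility list leaves it out for prior DCIS.

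The patient at issue has had DCIS before, is on risk-reduction therapy when the new lesion is biopsied, and stops between biopsy and enrolment. She is off therapy at enrolment, so I.4 is met. Her Sample #1 was taken under endocrine therapy and her Sample #2 without it. Ki-67 and the other markers may move because of the withdrawal as well as because of palbociclib, and her pair cannot separate the two. Group B offers no correction: patients choose their group, and section 2.3 plans no comparison of the groups on translational changes.

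**Working it through.** **1. The rules side by side**

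| Provision | Prior DCIS | Prior invasive cancer | On the signed checklist? |
|---|---|---|---|
| I.4 | Off therapy now; no interval | At least 4 weeks before biopsy | Yes |
| 4.4.3 | At least 4 weeks before biopsy | At least 4 weeks before biopsy | No |
| E.5 | 4 weeks, but standard risk-reduction drugs not named | Same | Yes |

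No other criterion from I.1 to I.19 or E.1 to E.12 sets an endocrine washout.

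**2. Day count for a Group A patient who stops just after the biopsy**

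Inputs from section 3.1.1: biopsy to surgery at most about 28 days; surgery on Study Day 15 ± 1, that is 13 to 15 days after Day 1; enrolment to surgery at least about 18 days; surgery postponed 7 days for cytopenia.

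- Washout at biopsy: 0 days, against 28 under section 4.4.3.
- Longest time off therapy at palbociclib Day 1: 28 − 15 = 13 to 28 − 13 = 15 days.
- Longest time off therapy at surgery: 28 days, or 28 + 7 = 35 days if surgery is postponed.

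**3. Would the records show it?**

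Section 4.4 has the eCRF capture "All prior treatment or medication administered during the 30 days prior to enrollment". In Group A, enrolment falls at most about 28 − 18 = 10 days after biopsy, so the 30-day look-back includes the biopsy date. In Group B, surgery may fall up to 42 days after biopsy (section 3.1.1) and screening bloods are due at least 5 days before surgery (section 4.5.2.6). Screening can therefore run to day 42 − 5 = 37, and the look-back may miss the biopsy date.

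**4. Share of the data**

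One affected patient is 1/12 = 8.3% of the pairs in her group.

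**5. Illustration of the effect on the paired t-test**

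The plan states no power and no effect size, so there is no figure to reproduce. Assume paired differences distributed N(0.89, 1), n = 12, two-sided alpha 0.05. The noncentrality is 0.89 × √12 = 3.08 on 11 degrees of freedom, which gives power 0.80. The 0.89 was chosen to give that value and is not in the documents. One patient is then shifted by s SD (simulation, 400,000 replicates). With an opposing shift the mean effect becomes 0.89 − s/12.

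| s (SD) | Mean effect, opposing | Power, opposing | Power, same direction | Rejection rate, no true change |
|---|---|---|---|---|
| 0.25 | 0.869 | 0.78 | 0.82 | 0.05 |
| 0.5 | 0.848 | 0.76 | 0.83 | 0.05 |
| 1 | 0.807 | 0.69 | 0.85 | 0.05 |
| 2 | 0.723 | 0.51 | 0.85 | 0.05 |

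The result depends on the assumed effect. One opposing 1 SD shift lowers power from 0.35 to 0.24 if the true effect is 0.5 SD, and from 0.97 to 0.93 if it is 1.2 SD. With no true change, one such patient does not raise the false-positive rate.

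**The case against.** The strongest reply is that the rule exists and is merely not repeated. A patient who follows section 4.4.3 also satisfies I.4, and section 8.8 requires the study to be run as the approved protocol describes. E.4 excludes patients unable to comply with study requirements, and an investigator could apply it to someone whose biopsy was taken on tamoxifen. E.5 can be read so that its agonists and antagonists extend to estrogen, which might reach tamoxifen and raloxifene. Section 4.4.3 also uses advisory wording.

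There are safeguards too. The eligibility packet must hold "Clinic notes containing information on ECOG PS, previous and current treatments", Appendix F asks for a "Concomitant medication list", and the project manager verifies eligibility before a study ID is issued. The case is narrow, and in a small descriptive study such a pair could be flagged and described separately.

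Much of this stands as a limit on weight. The affected patient would probably be recognised, the number may be zero, and the power figures follow from assumed inputs. It does not close the gap. E.4 states no washout. E.5 leaves aromatase inhibitors out on either reading. The packet and the eCRF document exposure but exclude no one. The people verifying eligibility check against the listed criteria, and those do not contain the interval. Advisory or not, section 4.4.3 sets a condition for prior DCIS that I.4 does not, while I.4 states it in full for prior invasive cancer.

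**Conclusion.** The inconsistency holds. Applied as written, the checklist admits a prior-DCIS patient whose baseline core was taken on a standard risk-reduction drug, contrary to section 4.4.3. No listed criterion states the washout that would keep her out.

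Severity is minor. The harm is confined to the pairs of such patients, each 8.3% of a group. The frequency of these cases and the size and direction of any withdrawal shift are not in the documents, and section 6.1 describes a mostly descriptive analysis. The power figures are illustrative and carry no weight in this rating. The conclusion rests on the text alone, with two premises: that the trial is usually offered after biopsy, as section 4.5.2.1 says, and that risk-reduction therapy means the agents listed in section 1.1.

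**What to change.** By amendment, extend the prior-DCIS clause of I.4 so that risk-reduction endocrine therapy must have stopped no less than four weeks before the diagnostic biopsy. Make the change in the synopsis, section 4.1.1 and the Appendix E checklist, so that all three agree with section 4.4.3 and with the clause for prior invasive cancer.

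The cost is one phrase in three places. An occasional candidate will be turned away, but only one whom section 4.4.3 already means to keep out.
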